6.8 Guidelines for Common Toxicities

6.8.1 Hydration During the Treatment Period

Because of the high tumor load the subjects should receive adequate hydration according to institutional guidelines.

6.8.2 Fever Management

Nonsteroidal anti-inflammatory drugs (NSAIDs) should be avoided if possible because they are a potential cause of endothelial stress and could potentially affect T-cells that

are required for blinatumomab action. For symptomatic relief of fevers due to any cause (ie, infection, drug fever) the recommended first choice agents for fever management are paracetamol/acetaminophen and/or dexamethasone. The dexamethasone dose should be reduced step-wise as soon as the fever is resolved. If these are not sufficiently effective, pethidin/meperidine is recommended. For pethidin/meperidine, adequate anti-emetic prophylaxis should be administered. The treating physician should also use their clinical judgment to determine the underlying cause of the fever and treatment.

6.8.3 Additional Treatment for Special Subject Populations

Subjects who enter the study who previously underwent alloHSCT and present with a medical history of GvHD must receive antifungal prophylaxis.

For subjects with a high risk for CMV infection [prior CMV re-activation or risk constellation in prior alloHSCT (donor: CMV negative, recipient: CMV positive)], one of the following measures should be performed:

- Intensive (2x/week) CMV-PCR follow-up with early therapeutic intervention if positive or
- Prophylactic CMV treatment.

6.9 Concomitant Therapy

Throughout the study, investigators may prescribe any concomitant medications or treatments deemed necessary to provide adequate supportive care except for those listed in [Section 6.10](#).

6.10 Excluded Treatments During Study Period

The following medications are not permitted during a subject's participation (including the induction, consolidation treatment) of this study:

- Any anti-tumor therapy other than the protocol specified therapy (ie, radiation therapy, immunotherapy, cytotoxic and/or cytostatic drugs);
- Chronic systemic (> 7 days) high-dose corticosteroid therapy (dexamethasone > 24 mg/day or equivalent); any other immunosuppressive therapies (except for transient use of corticosteroids);
- Any other investigational agent

6.11 Medical Devices

Blinatumomab must be administered using infusion pumps approved for use by the appropriate regulatory authorities for the country in which the subject is undergoing treatment, in both the inpatient and outpatient setting.

Approved

Blinatumomab infusion for solution will be prepared in bags for IV infusion and delivered through infusion lines that are both compatible with the IP as described in the IPIM.

Additional details for the use of the above mentioned medical devices and specific set of device specifications are provided in the IPIM.

Other non-investigational medical devices may be used in the conduct of this study as part of standard care. Other medical devices (eg, syringes, sterile needles, alcohol prep pads), that are commercially available are not provided or reimbursed by Amgen (except, if required by local regulation). The Investigator overseeing the conduct of the study at each respective institution will be responsible for obtaining these supplies.

6.12 Product Complaints

A product complaint is any written, electronic or oral communication that alleges deficiencies related to the identity, quality, durability, reliability, safety, effectiveness, or performance of a drug(s) or device(s) after it is released for distribution to market or clinic by either Amgen or by distributors and partners for whom Amgen manufactures the material. This includes any drug(s) or device(s) provisioned and/or repackaged /modified by Amgen. Drug(s) or device(s) includes investigational product. Any product complaint(s) associated with an investigational product(s) or non-investigational product(s) or device(s) supplied by Amgen are to be reported according to the instructions provided in the IPIM.

6.13 Contraceptive Requirements

6.13.1 Female Subjects

A female is considered of childbearing potential unless she has undergone a hysterectomy, bilateral salpingectomy, bilateral oophorectomy, or is postmenopausal.

Postmenopausal is defined as:

- A postmenopausal state is defined as no menses for 12 months without an alternative medical cause. (A high follicle stimulating hormone level in the postmenopausal range may be used to confirm a postmenopausal state in women not using hormonal contraception or hormonal replacement therapy [HRT]. However, in the absence of 12 months of amenorrhea, a single follicle stimulating hormone measurement is insufficient).
- Females on HRT and whose menopausal status is in doubt will be required to use 1 of the non-hormonal highly effective contraception methods if they wish to continue their HRT during the study. Otherwise, they must discontinue HRT to allow confirmation of postmenopausal status before study enrollment.

Female subjects of childbearing potential must agree to practice sexual abstinence or use an acceptable method of effective contraception during the treatment and for an additional 48 hours after the last dose of CIVI blinatumomab.

Acceptable methods of contraception include:

- Combined (estrogen and progestogen) or Progestogen-only hormonal methods given via oral, intravaginal, transdermal, injectable, or implantable route
- Intrauterine device (IUD)
- Intrauterine hormonal-releasing system (IUS)
- Bilateral tubal ligation/occlusion
- Vasectomized partner (Provided that partner is the sole sexual partner of the female subject of childbearing potential and that the vasectomized partner has received medical assessment of the surgical success)
- Sexual abstinence (Defined as refraining from heterosexual intercourse during the entire period of risk associated with the study treatments. The reliability of sexual abstinence must be evaluated in relation to the duration of the trial and the preferred and usual lifestyle of the subject.)
- Double barrier method: the male uses a condom and the female may choose either a cervical cap, diaphragm, or contraceptive sponge with spermicide (A female condom is not an option due to the risk of tearing when both partners use a condom.)

Female subjects of childbearing potential must receive pregnancy prevention counseling and be advised of the risk to fetus if they become pregnant during treatment and for an additional 48 hours after the last dose of CIVI blinatumomab.

Additional medications given during treatment with blinatumomab may alter the contraceptive requirements. These additional medications may require female subjects use highly effective methods of contraception and for an increased length of time. In addition, male subjects may also be required to use contraception. The investigator is to discuss these contraceptive changes with the subject.

If a female subject is suspected of being pregnant, the protocol-required therapies must be stopped immediately and may not be resumed until absence of pregnancy has been medically confirmed.

6.13.2 Unacceptable Methods of Birth Control for Women Subjects

Birth control methods that are considered unacceptable in clinical trials include: periodic abstinence (calendar, symptothermal, post-ovulation methods), withdrawal (coitus interruptus), spermicides only, and lactational amenorrhea method.

7. STUDY PROCEDURES

Refer to the Schedule of Assessments ([Table 9](#)) for an outline of the procedures required at each visit. Study procedures for days 1 through day 3 should occur as scheduled. Beginning with Day 8, all study procedures have a window of ± 1 day, unless otherwise noted.

Refer to the applicable supplement manuals (eg, IVRS/IWRS manual, laboratory manual and eCRF completion guidelines) for detailed data collection and procedural guidance.

7.1 Schedule of Assessments

Approved

Table 9. Schedule of Assessments

Examination	Screening / Pre-Phase	Treatment Period: Schedule for Each Cycle of Protocol-Specified Therapy						SFU Visit	Long-term FU Efficacy/Survival
		Day (D)	Screening ≤ 21 days	D1 ^a	D2	D3	D8		
Informed Consent	X								
Inclusion/Exclusion Criteria	X								
Medical History/Demographics	X								
ECOG Performance Status Assessment	X							X	
Neurological Examination	X	X						X	
Physical Examination	X	X	X		X	X	X	X	
Vital Signs & Temperature ^b	X	X	X		X			X	
Height & Weight ^c		X						X	
Lumbar Puncture/Intrathecal prophylaxis ^m	X ^o						X		
Bone Marrow Aspirate	X ^{d,o}						X	X ^d	X
Chemistry	X	X	X		X	X	X	X	
Coagulation		X	X					X	
Hematology with Differential	X	X	X		X	X	X	X	X
Urinalysis		X						X	
Creatinine Clearance ^e	X								
Lymphocyte Subsets ^f		X	X				X	X	(X)

Page 1 of 2

Footnotes provided on last page of table.

Approved

Table 9. Schedule of Assessments

Examination	Screening / Pre-Phase	Treatment Period: Schedule for Each Cycle of Protocol-Specified Therapy						SFU Visit	Long-term FU Efficacy/Survival
		D1 ^a	D2	D3	D8	D15	End of treatment cycle (D29 + 3days) ⁿ		
Day (D)	Screening ≤ 21 days							30 days (± 3 days) after protocol specified therapy	Every 3 months (± 1 month)
Immunoglobulins (IgG) ^g		X					X	X	
Pregnancy Test (urine or serum)	X							X	
Anti-blinatumomab antibodies ^h		X					X	X	
Intensive Pharmacokinetic Sample ⁱ		X	X			X	X		
Non-intensive Pharmacokinetic Sample ⁱ			X			X			
Cytokine ^l		X	X	X					
EORTC QLQ-C30 ^k		X			X	X	X	X	
Protocol-Required Therapy		Blinatumomab							
Concomitant Medication		Continuously throughout the whole core study							X
Disease Related Events/Adverse Events/Serious Adverse Events		Continuously throughout the whole core study							
Disease/Survival Status ^j									X

Page 2 of 2

ALL = acute lymphoblastic leukemia; BM = bone marrow; CSF = cerebrospinal fluid; ECOG = Eastern Cooperative Oncology Group;
 EORTC QLC-C30 = European Organization for Research and Treatment of Cancer Quality of Life Questionnaire C30; FU = follow-up; PK = pharmacokinetics;
 SFU = safety follow-up; ULN = upper limit of normal

^a All procedures completed on Day 1, must be completed before the initiation of protocol-specified therapy.

^b Vital signs (ie, systolic/diastolic blood pressure, heart rate, and respiratory rate) and temperature collected every 12 hours during cycle 1, day 1 (D1) and day 2 (D2), once daily on D1 and D2 for each subsequent cycle. Vital signs collected at cycle 1, day 8 (D8) only if dose step is performed and the SFU visit (± 3 days). Subject must be in a supine position in a rested and calm state for at least 5 minutes before blood pressure assessments are conducted. If the subject is unable to be in the supine position, the subject should be in most recumbent position as possible.

^c Height and weight performed pre-dose at baseline (Cycle 1 D1) only. Weight performed at SFU visit (± 3 days) only.

Approved

- ^d ALL BM assessments have + 3 days window during treatment phase. BM assessments at Screening: sample has to be taken prior to treatment start. Bone marrow aspirate/biopsy will be performed at the SFU visit (± 3 days), if the subject ended treatment for any other reason than relapse and has not had a bone marrow aspirate/biopsy performed within 6 weeks (± 3 days) of this visit. If a subject has not relapsed by day 29 (D29) of their last treatment cycle, BM aspirate should be performed every 3 months (± 1 month) until relapse.
- ^e Calculation of creatinine clearance only required if screening creatinine is ≥ 1.5 ULN.
- ^f Lymphocyte subsets will be collected at baseline (before first dose on Cycle 1 D1), at cycle 1 (24 hours after the beginning of the infusion [D2] and at the end of the infusion), and at the SFU visit. If B cells have not recovered (number of CD19-positive cells is 90 to 570 per μL) at the SFU visit lymphocyte subsets will also be collected 6 months (+3 months) after the SFU visit.
- ^g Immunoglobulin (IgG) samples will be collected pre-dose at baseline (Cycle 1 D1), at D29 (+3) days of each treatment cycle, and the SFU visit (± 3 days).
- ^h Anti-blinatumomab antibody samples are collected at baseline (before first dose on Cycle 1 D1), on D29 after the completion of cycle 2, and at the SFU visit (± 3 days). See [Section 7.8](#) for details regarding additional samples needed if Anti-blinatumomab antibody sample is positive at SFU.
- ⁱ Intensive PK (20 subjects): only within the first 2 treatment cycles. In cycle 1, samples will be taken prior to treatment start (prefer day 1, acceptable on day -1), and during infusion on day 1 (2 hours, 6 hours, 10 hours, ± 30 minutes), any time during day 2 and day 15 as well as on day 29 within 2 hours prior to the end of infusion and after the end of infusion at 3 hours (± 30 minutes) and 6 hours (± 30 minutes). In cycle 2, samples are collected at any time on day 2, day 15 and within 2 hours prior to end of infusion on day 29.
Non-intensive PK (rest of study population): PK samples will be collected on D2 and D15 in both cycle 1 and cycle 2 at the same time as other blood samples scheduled.
- ^j Subjects who did not respond to or relapsed after protocol-specified therapy and are being followed in long-term follow-up will only undergo a telephone contact to determine survival status by either the research investigational site or treating physician and collection of anti-leukemic treatment concomitant medications. Bone marrow and hematology assessments are required only for subjects who remain in remission.
- ^k EORTC QLQ C30 should be completed on D1, D8, D15, and D29 during Cycle 1; D1, D15, and D29 during cycle 2 and each consolidation cycle, and at the SFU visit (± 3 days).
- ^l Cytokine samples will be taken prior to treatment start (baseline), day 1 at 6 hours after infusion start and at any time on day 2 and day 3 in cycle 1.
- ^m Intrathecal prophylaxis within 14 days before the start of protocol-specified therapy AND following each treatment cycle (after BM aspirate on D29).
- ⁿ In case of premature treatment discontinuation, the end of treatment assessments should be performed immediately except CSF examination/prophylaxis (see [Section 6.6](#) for details).
- ^o Standard of care procedures such as bone marrow aspiration/biopsy and lumbar puncture are not considered study specific. Standard of care procedures may be performed prior to informed consent and used to determine eligibility, but must occur within 21 days prior to starting treatment with blinatumomab, unless specified otherwise. The intrathecal chemotherapy needs to be administered within 14 days prior to starting treatment with blinatumomab.

Approved

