2.4 Blinatumomab Background

[figure not shown]
Blinatumomab is a murine recombinant single-chain antibody construct combining both the binding specificity for the pan B-cell antigen CD19 and the epsilon chain of the T-cell receptor/CD3 complex on one polypeptide chain. It is monomeric, not glycosylated and weighs approximately 55 kDa.

It belongs to a new class of bispecific antibody constructs called bispecific T-cell engagers (BITE®). Bispecific T-cell engagers have been designed to direct T-effector memory cells towards target cells. The proximity induced by the BITE® triggers target cell-specific cytotoxicity, which closely resembles standard cytotoxic T lymphocyte (CTL) activation. This T-cell-mediated target-specific killing is the therapeutic mechanism of action of blinatumomab ([Löffler et al, 2000](#); [Wolf et al, 2005](#)).

Blinatumomab specifically targets cells that express CD19, a marker solely expressed by B cells, including B-precursor ALL cells, with an affinity of 1.49×10^{-9} M. Blinatumomab recruits and activates T cells via a lower affinity interaction with CD3 ($KD = 2.6 \times 10^{-7}$ M). These activated T cells then induce a half-maximal target cell lysis ranging in vitro within a range of 1 to 1000 pg/mL (0.018 -18 pM), showing blinatumomab to be an extremely potent molecule ([Dreier et al, 2002](#)).

During the course of tumor cell elimination, activated T cells synthesize and secrete pro-inflammatory cytokines as tumor necrosis factor-alpha (TNF- α), interferon-gamma (IFN- γ), interleukin (IL)-6, and IL-2, which might induce symptoms such as fever or decreases of blood pressure. In vitro data demonstrate cytokine release as a result of blinatumomab-mediated activation, which can be attenuated by corticosteroids without impairing the cytotoxic activity. In vivo data indicate cytokine release to be most prominent following the first dose of blinatumomab.

Figure 2. Mode of Action of Blinatumomab

Due to its unique ability to redirect T cells via CD3 towards a CD19⁺ tumor cell lysis, blinatumomab can elicit repeated target cell elimination by cytotoxic T cells and a polyclonal response of previously primed CD4⁺ and CD8⁺ T cells. The antitumor activity is effective within a wide range of effector to target (E:T) ratios.

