7.2.16 Lymphocyte Subsets

Immunophenotyping by flow cytometry to monitor peripheral blood changes in lymphocytes (B, T and natural killer [NK] cells), leukocyte populations (leucocytes, lymphocytes, monocytes, and granulocytes), T cells subsets, T cells activation markers as well as potential drug resistance mechanisms (T cells exhaustion markers, Tregs and immune checkpoint ligands) will be completed. Lymphocyte subsets will be collected at time points outlined in the Schedule of Assessments (Table 9).

If B-cell counts have not recovered at the SFU visit (recovered is defined as number of CD19-positive cells per μL is 90 to 570), another sample will also be taken 6 months (+3 months) after SFU visit for determination of lymphocyte subsets.

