10.1.1.4 Exploratory Endpoints

- Neurological adverse events
- Quantification and characterization of peripheral blood lymphocyte subsets
- Quantification and characterization of serum cytokines and chemokines

Approved

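### Table 9 footnote f and SAP 10.7.2 attach 90 to 570 CD19+ cells/µL to B cells that have not recovered, while Protocol 7.2.16 and 7.6 define the same range as recovered

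*Protocol*

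**What the plan says.** Four places describe the same conditional sample.

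- **Protocol 7.1, Table 9 footnote f:** the trigger, judged at the SFU visit, is worded "If B cells have not recovered (number of CD19-positive cells is 90 to 570 per" (the unit is µL). When it is met, subsets are measured once more 6 months (+3 months) later.
- **SAP 10.7.2:** repeats the footnote's trigger in the same words and refers to the Schedule of Assessments.
- **Protocol 7.2.16:** the condition opens "If B-cell counts have not recovered at the SFU visit (recovered is defined as number of CD19-positive cells per" (again µL), and the range that completes this definition is the same 90 to 570. A subject who does not meet it is due a further sample, with the same timing as in the footnote.
- **Protocol 7.6:** gives the same definition and the same action as 7.2.16, then points the reader to Section 7.2.17, which covers cytokines. Lymphocyte subsets are in 7.2.16.

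The sample serves one exploratory endpoint, "Quantification and characterization of peripheral blood lymphocyte subsets" (Protocol 10.1.1.4).

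**The concern.** All four places agree on the range, the timing and the action. They disagree on which state the range describes. In the footnote and the SAP, the bracket follows the words for non-recovery and reads as its definition. In 7.2.16 and 7.6, the bracket says expressly that it defines recovery.

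This matters because it is a working rule for drawing blood. Section 7 directs sites to Table 9 for what each visit requires, and 7.2.16 itself refers to Table 9 for its time points, so the clear definition sends the reader to the ambiguous one. The SAP contains only the footnote's version. In Table 9 the conditional sample is the only lymphocyte-subset entry after the SFU visit, and it cannot be recovered once its window has closed. If sites read different sections, the later samples could come from a mixture of opposite groups.

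**Working it through.** No sample-size, power or error-rate figure is involved, and the plan states no number to reproduce. The check is to apply each rule, as literally worded, to every possible CD19+ count at the SFU visit.

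| CD19+ cells/µL at SFU | 7.2.16 and 7.6 | Footnote f and SAP 10.7.2, read literally |
|---|---|---|
| Below 90 | Not recovered: sample due | Outside the stated range: no sample |
| 90 to 570 | Recovered: no sample | Inside the stated range: sample due |
| Above 570 | Outside the recovered range: sample due | Outside the stated range: no sample |

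1. **Agreement.** The three rows cover all counts, and the two rules disagree in each. The groups they select are complementary.

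2. **Intended meaning.** Protocol 2.4 says "Blinatumomab specifically targets cells that express CD19, a marker solely expressed by B cells". A count that has not recovered after treatment should therefore be low. Under the literal footnote, a subject with a count near zero would not be re-sampled, while one inside the range would be. Together with the explicit definition in two body sections, this supports 7.2.16 and 7.6 as the intended rule.

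3. **A gap in 7.2.16 itself.** Because recovered is a closed range, a count above 570 is literally not recovered and triggers the sample. Copying 7.2.16 unchanged would carry this into the footnote and the SAP.

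4. **What stays intact.** Table 9 and footnote f also schedule lymphocyte subsets at baseline, on day 2 and at the end of infusion in cycle 1, and at the SFU visit about 30 days after the last dose. None of these depends on the disputed trigger.

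**The case against.** The strongest reply is that this is a shorthand slip that few would act on. All four passages share one trigger in words: sample when B cells have not recovered. The footnote looks like 7.2.16 with the phrase introducing the definition left out, and two body sections give the definition in full. Section 7 describes Table 9 as an outline and refers sites to supplementary manuals for detail. Neither those manuals nor the separate biomarker analysis plan is available here, and they may state the rule correctly. The SAP sentence restates the schedule and does not direct collection.

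Much of this stands. A reader might infer that the wrong subjects will be sampled. The documents support only that they could be, if someone follows the footnote or the SAP to the letter. It does not remove the contradiction, because the schedule is operative text and the SAP has no correct version to set against it.

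Two further inferences are tempting and go too far.

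- **That the plan would have no other evidence on B-cell depletion after treatment, or could not describe recovery.** The SFU sample is itself taken after treatment and can be compared with baseline. IgG is also measured at that visit. Only the later time point is exposed.
- **That a head count of missed subjects can be given.** The documents state neither the number who will have an SFU sample nor the share who will be depleted. Footnote j limits long-term follow-up of non-responders and relapsed subjects to a telephone contact, although the B-cell paragraph in 7.6 is not expressly limited to subjects in remission. SAP 10.7.2 restricts this sampling to a subgroup, which footnote f does not. Survival also matters: after one full cycle the sample falls about 28 days + 30 days + 6 months, or roughly 8 months, from the start of treatment, against a median overall survival of 6.1 months in the earlier phase 2 study (Protocol 2.5.2).

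The wrong pointer in 7.6 is a minor matter. That section states the rule in full, so the pointer leads nobody to a wrong rule.

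**Conclusion.** The point holds as an internal inconsistency. Read literally, footnote f and SAP 10.7.2 reverse the trigger in 7.2.16 and 7.6 at every count, so a site or analyst following the former could sample recovered subjects and leave depleted ones without a later measurement.

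The importance is low: correcting it would be good practice, and no conclusion of the trial turns on it. At risk is one conditional time point of one exploratory endpoint. The SFU sample, the primary and secondary endpoints, the sample size and the error rates are unaffected. How many subjects would be misdirected cannot be estimated from the documents.

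The conclusion rests on two assumptions: that someone applies the footnote or SAP wording literally, and that no unseen manual or biomarker plan already overrides it. That 7.2.16 and 7.6 carry the intended meaning is an inference, though a well-supported one.

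**What to change.** - Reword Table 9 footnote f and the matching sentence in SAP 10.7.2 so that the bracket defines recovered, as in 7.2.16, and the sample is due when that definition is not met.
- In the same edit, state how a count above 570 cells/µL is classified, and apply the answer in 7.2.16 and 7.6 as well.
- Correct the cross-reference in 7.6 from 7.2.17 to 7.2.16.
- Have the biomarker analysis classify recovery by the 7.2.16 definition. If samples have already been drawn, report which rule the sites followed.

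The cost is one footnote, one SAP sentence, one clarification and one section number. It adds no samples beyond those 7.2.16 already requires.
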